### 4.2 Exclusion Criteria

- Currently taking metformin or other diabetic drugs
- Current or previous congestive heart failure, renal failure or liver failure
- Creatinine in Women of 1.4 or greater and Creatinine in Men of 1.5 or greater
- Existing untreated or prior cancer <5 years from diagnosis
- Received neo-adjuvant platinum-based chemotherapy or targeted therapy
- Receiving adjuvant platinum-based chemotherapy or targeted therapy after surgical resection

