#### Metformin as a chemoprevention agent

Metformin is an insulin sensitizer commonly used to treat diabetes. It lowers serum insulin levels and also directly inhibits cell growth. In addition to inhibiting gluconeogenesis, it also activates AMP kinase in epithelial cells by an LKB dependent mechanism. AMP kinase activation suppresses cell proliferation in malignant and nonmalignant cells by two different pathways -- inhibition of mTOR as well as through upregulation of p53/p21. Metformin may exert anti-tumour effects through both insulin dependent and insulin-independent mechanisms. Metformin also has indirect anti-proliferative effects related to lower systemic levels of insulin. The drug is well tolerated even by individuals without diabetes and does not cause hypoglycemia. Its main limited side effects are transient nausea and diarrhea. Lactic acidosis, a major adverse effect, is rare and seen only in those with concomitant renal failure or liver disease. Recent studies have shown its potential as a cancer prevention drug in cancers such as breast, prostate, pancreas, and colon.

In observational epidemiologic work, Evans et al. reported the risk of subsequent cancer diagnosis (all cancer types) was reduced in type 2 diabetics who received metformin (OR 0.85 for any vs. no metformin exposure). The protective effect increased with greater metformin exposure (measured as total dose prescribed or total duration of use). Additionally, Bowker et al. reported cancer mortality was lower in diabetics receiving metformin (vs. sulfonylureas or insulin, HR 0.50-0.77), but they did not study diabetics not receiving any drug therapy. Furthermore, while confirming lower cancer risk in diabetics receiving metformin (versus those not receiving metformin). Finally, Libby et al. have reported a significantly reduced risk of incident cancers (HR 0.63, 95% CI 0.53-0.75) in diabetics receiving metformin (versus those not receiving metformin); they recommended a randomized trial be conducted to "assess whether metformin is protective in a population at high risk for cancer". Although many preventative agents have been or are being explored in NSCLC, such as sulindac, celecoxib, selenium, and others, none to date have shown proven benefit.

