## 1.2 Dose Rationale and Risk/Benefits

Metformin is mainly associated with gastro-intestinal side effects. Previous trials have been done comparing metformin to a placebo that provided information about the frequency and magnitude of the main side effects and the contribution of GI symptoms to dropout rates. It was found that gastrointestinal toxicity occurred more frequently in patients receiving metformin than placebo. However lower doses of metformin (our dose is 1700mg/day) lead to less drop out than doses  $\leq$  2000mg/day. All patients are unlikely to respond equally to the chemoprevention effects of metformin. Evaluation of metformin response in vitro using lung epithelial cells derived from iPSCs offers a model to develop strategies for individualized chemoprevention.

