## 3 Study Design

### 3.1 General Design

Patients will be identified and enrolled from Thoracic Surgical Clinics. Patients will undergo surgical resection with the collection of tumor tissue, normal lung tissue, blood, and skin biopsies. For patients enrolled in the study that were found to have stage IA-IIIA SCC, starting less than 90 days from the time of surgery, patients will be randomized to receive either 850 mg po BID of metformin or observation. Metformin dosing will include a 4 week ramp up of 850 mg po daily prior to starting the BID dose, for a total of 6 months of Metformin. Patients will be followed for 2 years from the time of surgery to evaluate 2-year RFS. We plan to randomize a total of 100 patients (50 per arm), such that 90 patients are evaluable for the primary endpoint.

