## 4 Subject Selection Enrollment and Withdrawal

### 4.1 Inclusion Criteria

- Suspected or biopsy proven Stage IA-IIIA lung squamous cell carcinoma (must be proven SCC at the time of surgery)
- Medically fit for surgical resection (based on surgeon assessment)
- Current or prior smoker
- Age > 18 years old
- Both Male and Female
- Willing and able to consent to study, undergo study interventions, and take study drug
- ECOG performance status 0, 1, 2
- Subject must start Metformin within 90 days of surgery.

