### **5.6 Prior and Concomitant Therapy**

The subject's medications will be collected and reviewed prior to initiating the metformin or observation therapy to check for prior diabetes treatment. Subjects will be excluded if they are receiving treatment with diabetic agents. During the monthly telephone call the study coordinator will assess for any concomitant treatments with diabetic agents.

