### **General Physical Examination Findings**

At screening, any clinically significant abnormality should be recorded as a preexisting condition. At the end of the study, any new clinically significant findings/abnormalities that meet the definition of an adverse event must also be recorded and documented as an adverse event.

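### Section 1.1 ties lactic acidosis to liver disease, but 4.2 excludes only liver failure, so known significant liver disease short of failure remains eligible for metformin

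*Combined protocol and SAP*

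**What the plan says.** The background on metformin in section 1.1 describes the serious risk of the drug in one sentence: "Lactic acidosis, a major adverse effect, is rare and seen only in those with concomitant renal failure or liver disease".

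Section 4.2 then lists the organ conditions that bar entry: "Current or previous congestive heart failure, renal failure or liver failure". For the kidney it adds a laboratory limit: "Creatinine in Women of 1.4 or greater and Creatinine in Men of 1.5 or greater". It gives no further hepatic item.

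Section 3.1 plans to randomize 100 patients, 50 to each arm. The metformin arm takes 850 mg daily for four weeks and then 850 mg twice daily, for six months in all. Section 6.3 has eligibility assessed again at Visit 3, before randomization.

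**The concern.** The risk statement and the entry rule use different words for the liver. Liver disease is a wider class than liver failure: cirrhosis or active hepatitis can be present, known and clinically important without failure. The plan names the wider class as a setting for a major adverse effect and then excludes only the narrower one.

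What is at stake is the safety of individual patients in the metformin arm. Someone in a group that the plan itself links to lactic acidosis could be given six months of the drug without any breach of the protocol. The comparison of 2-year recurrence-free survival is not at stake.

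**Working it through.** No arithmetic applies. The check sets the risk statement beside the entry rule and then looks for any other text that would close the gap.

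**Kidney.** Section 1.1 names renal failure. Section 4.2 excludes renal failure, current or previous, and adds creatinine limits of 1.4 for women and 1.5 for men. The rule covers the stated risk and goes beyond it.

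**Liver.** Section 1.1 names liver disease. Section 4.2 excludes liver failure, current or previous, and nothing else. The rule covers only part of the stated risk.

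**Other text that might close the gap:**

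- 4.1 (inclusion) asks for fitness for resection as the surgeon judges it, ECOG status 0 to 2, and a subject willing and able to take the study drug. None of these is specific to the liver. Fitness for an operation is a different question from suitability for six months of metformin.
- 5.6 has a medication review before treatment, but its stated purpose is narrow: "The subject's medications will be collected and reviewed prior to initiating the metformin or observation therapy to check for prior diabetes treatment".
- 6.3 reassesses eligibility at Visit 3. It applies the criteria in 4.1 and 4.2, so it carries over the same hepatic rule.
- 8.1, on physical examination findings, says: "At screening, any clinically significant abnormality should be recorded as a preexisting condition". That is a recording rule. No criterion turns the record into an exclusion.
- 4.4.1 (withdrawal) lists new diabetes, non-adherence and the subject's own decision. None is hepatic.
- 6.1 to 6.5 (visits, calls and follow-up) name no hepatic check.
- 8.2 and 8.4 provide for questioning about adverse events at each contact and for oversight by the principal investigator. Both act after entry and neither sets an entry criterion.

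**Is the narrower threshold explained?** Section 1.2, which covers dose and risk, opens with "Metformin is mainly associated with gastro-intestinal side effects" and goes on to gastrointestinal toxicity and dropout. It gives no reason for placing the hepatic threshold at failure.

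**Result.** Take a patient with stage IA-IIIA squamous cell carcinoma, known cirrhosis without past or present failure, creatinine below the limit and every other criterion met. Followed exactly, the plan records the cirrhosis as a preexisting condition and then randomizes the patient, possibly to metformin.

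**The case against.** The best case for the sponsor is that one background sentence is not an eligibility rule. It says where lactic acidosis is seen; it does not say that every grade of liver disease carries the risk, and it calls the event rare. Surgeons may in practice turn away many patients with serious liver disease, and the requirement that a subject be able to take the study drug leaves room for clinical judgment. Monthly calls to the metformin arm ask about adverse events and new diagnoses, and the principal investigator oversees safety.

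Most of this stands, and it keeps the point minor. It does not remove the mismatch. The safeguards are either discretionary and not specific to the liver, or they act only once the patient is on the drug.

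A reader might infer three stronger things that the documents do not support:

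- *That 4.2 needs a liver-test limit to match the creatinine limit.* The creatinine limit goes beyond what 1.1 states, so its presence does not make a hepatic counterpart necessary. The documents supply no value for such a limit. If it were applied only where results happened to be on record, two identical patients could be treated differently.
- *That the creatinine used for entry could be out of date.* Section 6.3 reassesses eligibility before randomization, and nothing says that an older value is carried forward. The age of the sample is operational detail, not an error in the plan.
- *That the chance of enrolling such a patient, or of harm, can be stated.* Any such figure would need a prevalence that the documents do not give. Even a correct prevalence would describe enrollment and not lactic acidosis.

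**Conclusion.** The concern holds as a mismatch within the plan: 1.1 names liver disease, 4.2 excludes only liver failure, and nothing else in the documents sets a hepatic criterion. Known, clinically significant liver disease short of failure is therefore no bar to metformin.

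It is a minor, cheap safety improvement. The group exposed to the gap is some unknown part of the 50 patients assigned to metformin. With no prevalence and no event rate in the documents, its size cannot be narrowed further. A reader might infer that the trial knowingly exposes patients to a demonstrated hazard. The text does not support that, because it calls the event rare and does not grade liver disease by risk. Sample size, power and error rates are unaffected.

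The conclusion rests on reading liver disease in its ordinary sense, as wider than liver failure, and on taking the eligibility list as complete.

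**What to change.** In 4.2, replace the words for liver failure with: *liver failure or known clinically significant liver disease, including cirrhosis or active hepatitis*. Judge it from the medical history at the Visit 3 eligibility check that 6.3 already requires, before the randomization envelope is opened.

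The word *known* keeps this to history already available, so no new test, visit or form is needed. *Clinically significant*, a term that 8.1 already uses, leaves trivial liver findings eligible, and the two named conditions make clear what must be excluded at a minimum. Undiagnosed liver disease would remain eligible; the change does not claim to find it.

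The cost is a few more exclusions. Each one means that one more otherwise eligible patient has to be found to reach 100 randomized. This slightly affects accrual, whose feasibility is part of the first primary objective. Because the exclusions fall before randomization, they apply to both arms alike and do not bias the comparison.

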### 4.3 Subject Recruitment, Enrollment and Screening

- From the Principal Investigator or Co-Investigator clinical practices
- Evaluation of inclusion/exclusion criteria
- Informed consent

### 4.4 Early Withdrawal of Subjects

#### 4.4.1 When and How to Withdraw Subjects

- Subject develops a diagnosis of diabetes
- Failure of subject to adhere to protocol requirements
- Subject decision to withdraw from the study (withdrawal of consent)

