#### 4.4.2 Data Collection and Follow-up for Withdrawn Subjects

Even though a subject has withdrawn from the study, it may be important to collect some follow-up or survival data on such subjects throughout the protocol defined follow-up period. Such data is important to the integrity of the final study analysis since early withdrawal could be related to the safety profile of the study drug. If a subject withdraws consent to participate in the study, for subject safety reasons, attempts should be made to obtain permission to collect follow up information whenever possible.

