### **5.5 Subject Compliance Monitoring**

Subjects will be provided a medication diary in which they should track their administration of the metformin. The study coordinator will make a monthly telephone call to assess the subject's compliance. Subjects who are found to be less than 90% compliant will be counseled in the importance of taking the treatment daily and the PI will be notified.

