### **6.5 Half Yearly Follow Up**

The subjects will be followed every 6 months following surgery for a total of 2 years. At the time of the first 6 month follow up the subjects receiving metformin will return any unused study drug and drug reconciliation will occur.

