## 7 Statistical Plan

### 7.1 Statistical Methods

All patients meeting the eligibility criteria, and who started treatment, will be considered evaluable for the 2 year RFS rate endpoint. The proportion of 2 year RFS rates (along with the 95% confidence interval) will be estimated within each arm by the number of patients who are recurrence-free and alive at 2 years divided by the total number of evaluable patients in each arm, and compared using a chi-squared test.

Clinical data regarding recurrence-free survival (RFS) will be utilized for development of the metformin sensitivity index. Data collected will be summarized using descriptive statistics, including mean and standard deviation and median and inter quartile range for continuous variables, and using frequencies and percentages for categorical variables. Logistic regression models will be used to assess the impact of metformin sensitivity index metrics, treatment, and the interaction between the metformin sensitivity index metrics and treatment on the 2 year RFS status as the outcome of interest.

Adverse events (AEs) will be compared between metformin and placebo using CTCAE version 4. To evaluate the AE profiles associated with each intervention arm, the maximum grade for each type of AE will be recorded for each participant and frequency tables will be reviewed to determine the overall patterns. The number and severity of AEs (overall and by intervention group) will be tabulated and summarized across all grades. Chi-square tests will be used to compare the AE rates between metformin and placebo.

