## **8.2 Recording of Adverse Events**

At each contact with the subject, the study team must seek information on adverse events by specific questioning and, as appropriate, by examination. Information on all adverse events should be recorded immediately in the source document, and also on the appropriate adverse event worksheet. All clearly related signs, symptoms, and abnormal diagnostic, laboratory or procedure results should be recorded in the source document.

All adverse events occurring during the study period must be recorded. The clinical course of each event should be followed until resolution, stabilization, or until it has been ultimately determined that the study treatment or participation is not the probable cause. Serious adverse events that are still ongoing at the end of the study period must be followed up, to determine the final outcome. Any serious adverse event that occurs after the study period and is considered to be at least possibly related to the study treatment or study participation should be recorded and reported immediately.

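### Section 4.4.1 takes subjects off study for new diabetes or non-adherence without requiring further follow-up, so 2-year recurrence status may be lost for subjects who never refused it

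*Combined protocol and SAP*

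**What the plan says.** Section 4.4.1 gives three grounds for withdrawal: a new diagnosis of diabetes, "Failure of subject to adhere to protocol requirements", and the subject's own withdrawal of consent. Only the third is a refusal by the subject.

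For subjects already withdrawn, section 4.4.2 says that "it may be important to collect some follow-up or survival data on such subjects throughout the protocol defined follow-up period". It gives the reason, which concerns metformin: "Such data is important to the integrity of the final study analysis since early withdrawal could be related to the safety profile". Its one active step, seeking permission to collect follow-up, is tied to subjects who withdraw consent.

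Other sections bear on the point:

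- **Section 6.5:** "The subjects will be followed every 6 months following surgery for a total of 2 years". It does not say whether this continues after withdrawal.
- **Section 5.5:** "Subjects who are found to be less than 90% compliant will be counseled in the importance of taking the treatment daily", and the principal investigator is told. No level of non-compliance is named at which section 4.4.1 applies.
- **Section 7.1:** "All patients meeting the eligibility criteria, and who started treatment, will be considered evaluable for the 2 year RFS rate endpoint". The rate in each arm is estimated "by the number of patients who are recurrence-free and alive at 2 years divided by the total number of evaluable patients in each arm". The arms are then compared by a chi-squared test.
- **Section 9.1:** for subjects who revoke authorization, the site should try to obtain permission to record at least whether they are alive. Recurrence is not mentioned.

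**The concern.** The plan treats stopping the drug and leaving the study as one event. A subject who develops diabetes or takes the capsules poorly may be perfectly willing to be seen every six months, yet section 4.4.1 allows the investigator to withdraw that subject, and nothing then obliges anyone to establish recurrence status at 2 years. Subjects withdrawn by the investigator have less explicit provision than those who withdraw consent.

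Comparing 2-year RFS between the arms is listed among the primary objectives in section 2. Under section 7.1 a withdrawn subject who started treatment stays in the denominator but can reach the numerator only if known to be alive and recurrence-free. There is no censoring and no rule for unknown status.

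Loss may also be unequal. Non-adherence to drug can occur only on metformin, and section 6.4 schedules monthly calls about compliance and new diagnoses only for that group. New diabetes and missed visits can occur in both arms. If unknowns are treated as failures and more of them are on metformin, the comparison is biased against metformin. If withdrawal is related to outcome, leaving the unknowns out is biased as well.

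**Working it through.** **Inputs from the protocol.** Section 3.1 plans 100 randomised, 50 per arm, so that 90 are evaluable; that is an implied allowance of 10%, since 90/0.90 = 100. Section 2 splits the 90 into 20 + 25 = 45 on metformin and 45 on observation. The planned shortfall of 10 does not clearly absorb the problem, because an eligible subject who starts treatment and is later withdrawn is still evaluable under section 7.1.

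**Assumptions.** The documents give no withdrawal rate, expected RFS or significance level. I assume equal true 2-year RFS p in both arms (50%, with 30% and 70% as a range), a two-sided 5% level, the chi-squared test without continuity correction, unknowns counted as failures unless stated, and withdrawal unrelated to outcome.

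**Spurious deficit.** Let uM and uO be the numbers with unknown status on metformin and observation. The expected observed rates are p(45 − uM)/45 and p(45 − uO)/45, so

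deficit = (uM − uO) × p / 45.

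At p = 0.5, 3 v 2 gives 1 × 0.5/45 = 1.1 points, and 5 v 0 gives 5 × 0.5/45 = 5.6 points.

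**Chance of wrongly favouring observation.** I enumerated all outcomes exactly, with binomial(45 − uM, p) and binomial(45 − uO, p) successes and 45 as each denominator, and summed the probability of a significant result against metformin.

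| True RFS | Unknown, metformin v observation | Deficit (points) | P(significant for observation) |
|---|---|---|---|
| 50% | 0 v 0 | 0 | 2.3% |
| 50% | 3 v 2 | 1.1 | 2.6% |
| 50% | 5 v 4 | 1.1 | 2.3% |
| 50% | 5 v 2 | 3.3 | 4.0% |
| 50% | 5 v 0 | 5.6 | 6.5% |
| 30% | 0 v 0 | 0 | 2.7% |
| 30% | 3 v 2 | 0.7 | 3.0% |
| 30% | 5 v 0 | 3.3 | 5.5% |
| 70% | 0 v 0 | 0 | 2.7% |
| 70% | 3 v 2 | 1.6 | 2.9% |
| 70% | 5 v 0 | 7.8 | 11.2% |

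**Unknowns excluded instead.** With 40 v 45 analysed, p = 0.5 and withdrawal unrelated to outcome, the expected deficit is 0 and the chance of a significant result is 2.6% in each direction.

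**Bounds without any missing-data assumption.** With m of 45 unknown, an arm's observed-sample RFS is determined only to within m/45: 2/45 = 4.4 points, 5/45 = 11.1 points. If follow-up continues off drug, this width is zero for these subjects.

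**The case against.** The best defence is that the intent to follow is already present. Section 4.4.2 exists to address withdrawn subjects, names the full follow-up window and says why the data matter. Sections 3.1 and 6.5 set two years of follow-up without excepting subjects off drug, and section 7.1 analyses treated subjects whatever their adherence. Section 9.2 lists hospital records and clinic charts among source documents, so a single site could often recover status. Poor compliance leads first to counselling, and metformin lasts only six months, so drug non-adherence can arise only in that window.

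All of this is fair, and it narrows the problem: section 4.4.1 permits withdrawal for non-adherence rather than triggering it at the first missed doses. It does not close the gap. Nothing requires the records to be searched, section 6.5 is silent on withdrawn subjects, and the separate, softer wording of section 4.4.2 suggests that the ordinary schedule no longer binds.

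The second objection is size. At 50% RFS the standard error of the difference is √(2 × 0.5 × 0.5/45) = 10.5 points, so even the 5.6-point deficit is about half a standard error. The total two-sided false-positive rate actually falls under near-equal loss, from 4.5% with none to 4.1% at 3 v 2 and 3.7% at 5 v 4, and reaches only 7.0% at 5 v 0. Counting unknowns as failures is my assumption and not a rule in section 7.1, and the trial is a pilot. These points stand. They limit how serious the matter is, not whether it is real.

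The adverse-event side is minor. Section 8.2 says that "Any serious adverse event that occurs after the study period and is considered to be at least possibly related to the study treatment" or to participation is still to be recorded and reported. Only other new events after withdrawal could be missed, and only if withdrawal ends the study period, which the protocol does not say.

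**Conclusion.** The concern holds, and the plan should be changed on this point. The protocol allows withdrawal from the study for two reasons that call only for a decision about the drug, does not require outcome follow-up afterwards, and keeps these subjects in the RFS denominator with no rule for unknown status.

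The size is conditional. With near-equal loss it is about 0.7 to 1.6 points over true RFS of 30% to 70%, with almost no change in error rates. With 5 unknown on metformin and none on observation, all counted as failures, it is 3.3 to 7.8 points, and the chance of wrongly favouring observation is 5.5% to 11.2% against about 2.3% to 2.7% with no loss. Material bias therefore needs either clearly unequal loss with unknowns counted as failures, or withdrawal related to outcome. Whether either would occur cannot be judged from the documents. Confidence is medium: the reading of the text is firm, but the numbers of withdrawals, the RFS rates and the handling of unknowns are all assumed.

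**What to change.** - **Section 4.4.1:** make new diabetes and non-adherence reasons to stop study drug only. Keep withdrawal of consent as the only reason to leave follow-up. The clinical decision to stop metformin stays with the investigator.
- **Section 4.4.2:** require the half-yearly follow-up of section 6.5 for recurrence, survival and adverse events to 2 years for every randomised subject who has not withdrawn consent.
- **Section 7.1:** keep the planned proportion and chi-squared test, and add a sensitivity analysis for any remaining unknown 2-year status, for example counting unknowns as failures in both arms and then excluding them from both arms.

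The cost is a rewording of two short sections, a brief addition to a third, a few more off-drug visits and a little extra analysis. The sample size, the planned estimate and the test do not change.
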